4.1.5 Blinding and procedures for unblinding

4.1.5.1 Blinding

Not applicable as this is an open-label single-arm trial.

4.1.5.2 Unblinding and breaking the code

Not applicable.

4.1.6 Packaging, labelling, and re-supply

For details of packaging and the description of the label, refer to the ISF. Re-supply of BI 836826 will be managed by an IRT system. To facilitate the use of IRT, the investigator will receive an IRT manual including all necessary instructions.

4.1.7 Storage conditions

BI 836826 drug supplies will be kept in their original packaging and in a secure limited access storage area according to the recommended storage conditions on the medication label. A temperature log must be maintained for documentation.

If the storage conditions are found to be outside the specified range, the CML (as provided in the list of contacts) and the Interactive Voice Response System/ Interactive Web-based Response System (IVRS/IWRS) must be contacted immediately.

For more details on BI 836826, please refer to the IB ([c01715907-08](#)) and to the ISF.

Ibrutinib will be stored under the conditions specified in the package insert. Excursions are permitted as described in the package insert.

4.1.8 Drug accountability

The Investigator and/or pharmacist and/or investigational drug storage manager will receive the investigational drug BI 836826 delivered by the Sponsor when the following requirements are fulfilled:

- Approval of the trial protocol by the Institutional Review Board (IRB)/ethics committee,
- Availability of a signed and dated clinical trial contract between the Sponsor and the head of the investigational site,
- Approval/notification of the regulatory authority, (e.g. Competent Authority),
- Availability of the curriculum vitae of the principal Investigator,
- Availability of a signed and dated CTP
- Availability of the proof of a medical license for the principal Investigator
- Availability of Form 1572

The Investigator and/or pharmacist and/or investigational drug storage manager must maintain records of the BI 836826 product's delivery to the trial site, the inventory at the site, the use by each patient, and the return to the Sponsor or alternative disposal of unused products.

These records will include dates, quantities, batch / serial numbers, expiry ('use- by') dates, and the unique code numbers assigned to the investigational product and trial patients. The Investigator / pharmacist / investigational drug storage manager will maintain records that

document adequately that the patients were provided the doses specified by the CTP and reconcile all investigational products received from the Sponsor. At the time of return to the Sponsor and/or appointed CRO, the Investigator / pharmacist / investigational drug storage manager must verify that all unused or partially used drug supplies have been returned by the clinical trial patient and that no remaining supplies are in the Investigator's possession.

4.1.8.1 Ibrutinib sourcing and accountability

Ibrutinib (Imbruvica) will not be supplied by Boehringer-Ingelheim. Sourcing of ibrutinib will be the responsibility of the patient and their insurance. Ibrutinib is the standard of care for patients with relapsed/refractory CLL who have received at least one prior therapy and will be prescribed by the investigator or the patient's physician. Site staff should request that patients bring their backbone medication (i.e., ibrutinib) supply to clinic visits to record quantities of capsules and to monitor dosing compliance. Unused drug should not be returned to Boehringer Ingelheim.

4.2 CONCOMITANT THERAPY, RESTRICTIONS, AND RESCUE TREATMENT

4.2.1 Rescue medication, emergency procedures, and additional treatment(s)

4.2.1.1 Rescue medication

Rescue medication in term of an antidote to reverse the action of BI 836826 is not available. Potential side effects of BI 836826 have to be treated symptomatically.

Rescue medication or antidote to reverse the action of ibrutinib is not available or referenced in the package insert ([R15-5127](#)). Side effects associated with ibrutinib have to be treated as described by the package insert and at the discretion of the Investigator.

4.2.1.2 Concomitant medication

All concomitant therapies to provide adequate care may be given as clinically necessary, unless given as anti-leukemia therapy. All concomitant treatments should be recorded in the eCRF except for vitamins or nutrient supplements. Trade name, indication and dates of administration of concomitant therapies will be documented. For parenteral nutrition during the trial, the components need not to be specified in detail. It should just be indicated as 'parenteral nutrition'. If a patient needs general anaesthesia, it will be sufficient to indicate 'general anaesthesia' without specifying the details. For glucocorticoids and growth factors, the dose should be captured in addition in the eCRF.

Concomitant therapy should be recorded in the eCRF during the screening and on-treatment period, starting at the date of signature of informed consent, and ending at the end of the Residual Effect Period (REP), 30 days after the last infusion of BI 836826 (see [Section 5.3.7](#)).

If a new anti-leukaemia treatment is started, it will be documented in the eCRF on a separate page of subsequent therapy, different from the concomitant therapies pages.

4.2.1.2.1 Pre-Medication prior to BI 836826 infusion

Pre-medication is mandatory 30-120 minutes prior to the administration of BI 836826 to mitigate the risk for IRRs. In case a contra-indication for one of the drug exists, the drug may be replaced or omitted. If BI 836826 has been well tolerated without signs of IRRs during cycle 2, the glucocorticoid dose may be reduced in Cycle 3 while the other drugs are maintained. The first step in cycle 3 may be a reduction from 100 mg to 50 mg prednisolone or equivalent. If the cycle 3 doses are tolerated without IRR, the glucocorticoid may be reduced to 25 mg prednisolone or equivalent prior to a subsequent administration in cycle 4. If BI 836826 is tolerated without IRR after pre-medication with prednisolone 25 mg or equivalent, acetaminophen and antihistamine in cycle 4, the investigator may individually decide whether to administer pre-medication in cycle 5 and subsequent treatment cycles and which of the recommended drugs to use.

All pre-medications with doses should be source documented.

If IRRs are still seen at later infusions, pre-medication triplet should continue to be used for all administrations.

Table 4.2.1.2.1:1 Premedication table

Cycle	Patients Requiring Premedication	Premedication	Completion Prior to BI 836826
1-2	all patients	Analgesic/Antipyretic p.o. or i.v. ¹ Antihistamine p.o. or i.v. ² Glucocorticoid i.v., equivalent to prednisolone 100 mg	60-120 minutes
3	all patients with IRR in the previous infusion and/or with ALC $\geq 25000/\mu\text{l}$	Analgesic/Antipyretic p.o. or i.v. ¹ Antihistamine p.o. or i.v. ² Glucocorticoid i.v., equivalent to prednisolone 100 mg	60-120 minutes
3	patients without IRR in previous infusion and ALC $< 25000/\mu\text{l}$	Premedication Level -1: Analgesic/Antipyretic p.o. or i.v. ¹ Antihistamine p.o. or i.v. ² Glucocorticoid i.v., equivalent to prednisolone 50 mg	30-120 minutes
4 and subsequent Cycles	patients with ALC $< 25000/\mu\text{l}$ and without IRR and premedication at level -1 at previous infusion	Premedication Level -2: Analgesic/Antipyretic p.o. or i.v. ¹ Antihistamine p.o. or i.v. ² Glucocorticoid i.v., equivalent to prednisolone 25 mg	30-120 minutes
5 and subsequent Cycles	patients with ALC $< 25000/\mu\text{l}$ and without IRR and premedication at level -2 at previous infusion	Premedication at the discretion of the investigator	

¹ equivalent to Acetaminophen/Paracetamol; ²1000 mg equivalent to diphenhydramine 50 mg i.v.

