4.1.4.1 BI 836826 infusion rates

Table 4.1.4.1: 1 provides a summary of planned and modified infusion rates. Pre-medication prior to each administration of BI 836826 is required [Section 4.2.1.2.1](#)

Table 4.1.4.1:1 Planned and modified infusion rates

Day of Treatment	Dose of BI 836826	Initial Rate of Infusion and Maximum Escalation Steps*	Maximum Allowed Infusion Duration	Maximum Allowed Infusion Rate
Cycle 1 Day 1	10 mg	2 mg/hr x 60 min Escalate by 1 mg/hr every 30 min as tolerated to maximum allowed rate**	24 hr	5 mg/hr
Cycle 1 Day 2	50% of target dose	≤ 50 mg/hr x 60 min Escalate by ≤ 50 mg/hr every 30 min as tolerated to maximum allowed rate**	24 hr	400 mg/hr
Cycle 1 Day 8	50% of target dose	≤ 50 mg/hr x 60 min Escalate by ≤ 50 mg/hr every 30 min as tolerated to maximum allowed rate**	24 hr	400 mg/hr
Cycle 1 Day 15	100% of target dose	≤ 50 mg/hr x 60 min Escalate by ≤ 50 mg/hr every 30 min as tolerated to maximum allowed rate**	24 hr	400 mg/hr
Cycle 2 Day 1 and subsequent Cycles	100% of target dose	≤ 50 mg/hr x 30 min, then ≤ 100 mg/hr x 30 min Escalate by ≤ 100 mg/hr as tolerated to maximum allowed rate**	24 hr	500 mg/hr

* Infusion rates may be adjusted and given extremely slowly over a longer period of time (not to exceed 24 hours) for patients with a White Blood Cell Count (WBC) ≥ 100 x 10⁹/L at the time of infusion,

** slower start rate or smaller increments allowed at investigator's discretion

Cycle 1 Day 1: BI 836826 “pre-dose” of 10 mg:

BI 836826 administration will start with a “pre-dose” of 10 mg on Day 1 of the first cycle. Pre-medication according to [Section 4.2.1.2.1](#) is mandatory. The initial infusion rate to mitigate the risk for severe infusion related reactions is 2 mg/h for the first 60 minutes. In the absence of infusion related reactions the rate can be escalated every 30 minutes by increments of 1 mg/h to a maximum rate of 5 mg/h.

In patients with a high risk for IRRs or TLS (e.g., a $WBC \geq 100 \times 10^9/L$ at the start of infusion), or occurrence of an IRR during the infusion, the infusion may be given extremely slowly over a longer period of time, but not exceeding 24 hours.

Cycle 1 Day 2 and Cycle 1 Day 8: BI 836826 at 50% of target dose:

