Pre-medication, according to [Section 4.2.1.2.1](#), is mandatory. The recommended initial infusion rate to mitigate the risk for severe IRRs should not exceed 50 mg/h for the first 60 minutes. The rate can be escalated every 30 minutes by increments of 50 mg/h or less to a maximum rate of 400 mg/h in the absence of IRRs. A slower start rate or smaller increments are possible based on individual risk assessment. Reductions in the infusion rate may be applied as indicated to ensure tolerability. In patients with a high risk for IRRs or TLS (e.g., a white blood cell count (WBC) $\geq 100 \times 10^9/L$ at the start of infusion), or occurrence of an IRR during the infusion, the infusion may be given extremely slowly over a longer period of time but not exceeding 24 hours.

Cycle 1 Day 15: BI 836826 at 100% of target dose:

Pre-medication, according to [Section 4.2.1.2.1](#), is mandatory. The recommended initial infusion rate to mitigate the risk for severe IRRs should not exceed 50 mg/h for the first 60 minutes. The rate can be escalated every 30 minutes by increments of 50 mg/h or less to a maximum rate of 400 mg/h in the absence of IRRs. A slower start rate or smaller increments are possible based on individual risk assessment. Reductions in the infusion rate may be applied as indicated to ensure tolerability. In patients with a high risk for IRRs or TLS (e.g., a $WBC \geq 100 \times 10^9/L$ at the start of infusion), or occurrence of an IRR during the infusion, the infusion may be given extremely slowly over a longer period of time but not exceeding 24 hours.

Cycle 2 Day 1 and subsequent cycles: BI 836826 at 100% of target dose:

In the absence of infusion related reactions during the administration of the previous full dose, the subsequent administration of BI 836826 is recommended to start at a rate of 50 mg/h or less for the first 30 minutes, followed by a rate of 100 mg/h or less for 30 minutes. Incremental steps thereafter may be larger depending on individual tolerability, but must not exceed 100 mg/h. A maximum rate of 500 mg/h is not to be exceeded. A slower start rate and smaller increments are possible based on individual risk. Reductions in the infusion rate may be applied as indicated to ensure tolerability. Pre-medication should be considered according to [Section 4.2.1.2.1](#).

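### The premedication text and table in Protocol Section 4.2.1.2.1 disagree on timing and on who may step down the steroid; Section 4.1.4.1 and SAP check D2 do not fully match them

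*Protocol*

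**What the plan says.** **Timing.** The running text of Protocol Section 4.2.1.2.1 opens: "Pre-medication is mandatory 30-120 minutes prior to the administration of BI 836826 to mitigate the risk for IRRs". It names no cycle. Table 4.2.1.2.1:1 has a column for completion before BI 836826. That column reads "60-120 minutes" for all patients in Cycles 1-2 and for the Cycle 3 row on the full 100 mg prednisolone-equivalent dose. The 30-120 minute window appears only in the two reduced-steroid rows.

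**Steroid step-down.** The text says: "If BI 836826 has been well tolerated without signs of IRRs during cycle 2, the glucocorticoid dose may be reduced in Cycle 3". The further steps in Cycles 4 and 5 also depend only on absence of IRR. The table assigns the full dose in Cycle 3 to "all patients with IRR in the previous infusion and/or with ALC" at or above 25000/µL, and the first reduction to "patients without IRR in previous infusion and ALC" below that threshold. It repeats the ALC condition for Cycle 4 and for investigator discretion from Cycle 5.

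**Status.** Protocol Section 4.1.4.1 begins: "Pre-medication prior to each administration of BI 836826 is required". Its paragraphs on the Cycle 1 infusions call premedication mandatory. Its paragraph on Cycle 2 Day 1 and later says: "Pre-medication should be considered according to" Section 4.2.1.2.1.

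**SAP.** Table 6.2:1, category D2, records premedication not given per protocol as an important protocol violation. The check runs until Cycle 6, after which premedication is left to investigator judgement.

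**The concern.** Premedication is one of the protocol's stated measures against IRRs (Sections 2.3 and 4.2.1.2.1). IRR was the most frequent adverse event in trial 1270.1, where three patients had a grade 3 reaction. Here a site can follow the text and breach the table in the first two cycles. It can also reduce the steroid in a patient whom one rule holds at full dose and the other does not.

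The stakes are consistent handling of patients still on treatment, and a clear reference for the premedication listing (SAP Section 7.3) and the D2 violation count in the report.

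**Working it through.** No figure in the plan needs recomputing. The check sets the passages side by side.

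**1. Timing, Cycles 1-2**
- Text window: 30 to 120 minutes, width 120 − 30 = 90 minutes.
- Table window: 60 to 120 minutes, width 120 − 60 = 60 minutes.
- Difference: 90 − 60 = 30 minutes. Premedication completed 45 minutes before a Cycle 1 infusion meets the text and breaches the table.
- Infusions covered (schedule in Table 4.1.1:1): four in Cycle 1 (Days 1, 2, 8, 15) and two in Cycle 2, so 4 + 2 = 6 per patient. The 12-cycle total is 4 + (3 × 2) + (8 × 1) = 18, which matches the synopsis. The conflict therefore covers 6 of 18 planned infusions, plus up to two in Cycle 3 for patients on the full-dose row.

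**2. Steroid step-down at Cycle 3 Day 1**

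| Patient | IRR at Cycle 2 Day 1 | IRR at Cycle 2 Day 15 | ALC | Text | Table |
|---|---|---|---|---|---|
| A | No | No | ≥25000/µL | may reduce | full dose |
| B | Yes | No | <25000/µL | condition not met | reduced level |

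Patient A differs because the text has no ALC condition. Patient B differs because the text looks back over the whole of Cycle 2 and the table only at the previous infusion. The disagreement runs in both directions, so neither rule is simply the stricter one. The ALC difference recurs at the Cycle 4 and Cycle 5 steps.

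**3. Required or considered**
- Section 4.1.4.1, opening: required before each administration.
- Section 4.1.4.1, Cycle 2 Day 1 onward: to be considered.
- Section 4.2.1.2.1: all three drug classes for all patients in Cycles 1-2, with discretion only from Cycle 5 and only for patients who meet the conditions.

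The considered wording does not fit Cycles 2-4, and the each-administration wording does not fit discretion from Cycle 5.

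**4. SAP D2**
- Protocol: a qualifying patient may go without premedication from Cycle 5.
- D2: a No answer for any standard premedication is checked until Cycle 6, with medical review of the comments.

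A permitted omission at Cycle 5 (and at Cycle 6, if the cut-off is inclusive) meets the automated trigger. It would be cleared only if the medical review overrides it.

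**5. Size of the IRR background.** From Protocol Section 1.2.1: 25/36 = 69% with any IRR and 3/36 = 8% with grade 3. Section 2.3 adds that 3 of 36 stopped treatment early because of IRRs.

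**The case against.** The strongest reply is that the passages can be read together. The 30-120 minute window contains both table windows, so a site that follows the table also meets the text on timing. The steroid wording is permissive, and the table can be taken as stating who qualifies. Section 4.1.4.1 refers the reader to Section 4.2.1.2.1, and its heading for Cycle 2 and later includes the cycles with discretion.

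Part of this stands. Because of the cross-reference, the required-or-considered point is lesser and confined mainly to Cycles 2-4. The envelope reading of the timing is possible, but the text presents its window as the mandatory one and does not defer to the table. The permissive reading of the steroid rule fails for patient B, whom the table steps down although the text's condition is not met.

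A reader might also infer more than the documents support:
- **That many patients will meet the ALC condition at Cycle 3, because lymphocytosis occurred in 77% on ibrutinib.** That figure (Section 1.2.2) means a rise of at least 50% and ALC above 5,000/mcL, and the table's threshold is five times higher. In 1270.1, BI 836826 lowered ALC by 50% or more in 20/25 patients and to below 4 × 10⁹/L in 14/25 (Section 1.2.1). A patient on schedule has had six infusions before Cycle 3. The documents give no count at or above 25000/µL.
- **That D2 cannot be applied at all.** Its trigger asks only whether standard premedication was received. It does not test minutes, ALC or steroid level, and it excludes no one from analysis. The cut-off mismatch is the specific D2 problem.
- **That dose finding is compromised.** Section 5.3.6.2 excludes IRRs of any grade from dose-limiting toxicity, and IRR rate is neither a primary nor a secondary endpoint.
- **That IRR rates will differ by site because of this.** The documents contain no data on that.

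**Conclusion.** The point holds as an inconsistency in operative safety instructions. The two main conflicts, on timing and on the step-down condition, both sit within Section 4.2.1.2.1 of the current protocol. The Section 4.1.4.1 wording and the D2 cut-off are secondary.

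Timing affects six infusions per patient on schedule. The number of patients affected by the step-down conflict cannot be derived from the documents. There is no direct effect on the dose-limiting toxicity count, the Bayesian model or the maximum tolerated dose.

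Recruitment is being stopped (Section 2.1), so few Cycle 1-2 infusions may remain, although the documents do not say how many. Current patients may continue treatment, and D2 still has to be applied in the report. A correction is therefore worthwhile but not critical. This conclusion assumes that text and table carry equal authority, since the protocol does not rank them.

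**What to change.** Reconcile the text of Protocol Section 4.2.1.2.1, its table and the two statements in Section 4.1.4.1 so that each cycle has:
- one premedication window, stating whether it refers to start or completion;
- one step-down condition, stating the IRR look-back and whether ALC counts;
- one status, required or discretionary.

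Then align the D2 cycle cut-off in SAP Table 6.2:1 with the result, and say whether the last cycle is included. The choice of clinical rule belongs to the sponsor and investigators, and none is proposed here.

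The cost is wording in the protocol and one line in the SAP. No change to the design, sample size or model is needed. If the protocol is not amended again, a written clarification to sites and a note in the report on which rule D2 was judged against would cover the analysis side.

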4.2.1.2.2 Tumor Lysis Syndrome (TLS) prophylaxis and monitoring

Patients at risk for TLS, e.g. with a high tumor burden or preexisting renal dysfunction, should receive prophylaxis for TLS prior to the initiation of treatment. These subjects must be well hydrated. It is desirable to maintain a fluid intake of approximately 2-3 liters per day for 1-2 days before the first 50% dose of BI 836826. Treatment with allopurinol (≥ 300 mg p.o./day) or a suitable alternative (e.g., rasburicase) starting ≥ 24 hours prior to the first infusion should be considered unless contraindications exist. Repeated prophylaxis with allopurinol and adequate hydration should be continued prior to each subsequent infusion, if deemed appropriate by the investigator. For all patients, electrolytes, fluid balance and renal function should be monitored and corrected. Supportive care should be administered, including dialysis, if indicated.

TLS will be classified and recorded according to CTCAE: Grade 3 (present), Grade 4 (life threatening consequences; urgent intervention indicated) and Grade 5 (death).

Clinical tumor lysis syndrome: is considered present if laboratory TLS is diagnosed and one or more of the following criteria is met:

- increased serum creatinine (≥ 1.5 times upper limit of normal)
- cardiac arrhythmia
- seizure

4.2.1.2.3 Antibiotics and antivirals

Prophylactic antibiotics and antivirals are allowed. For patients considered to have an increased risk for infections, prophylactic therapy is strongly recommended unless medically contraindicated. For restrictions on use of CYP 3A inhibitors, see [Section 4.2.2.1](#)

Prophylactic antiviral therapy, e.g. acyclovir 400 mg three times a day orally, should be considered for patients at risk for a herpes infection or reactivation, e.g. with a history of recurrent herpes virus infections, herpes infection during previous anti-tumour therapy, neutropenia and low CD4+ cell counts (< 200 cells/ μ l). For restrictions on use of CYP 3A inhibitors, see Section 4.2.2.1

Prophylaxis against *Pneumocystis jiroveci*, e.g. oral trimethoprim/sulfamethoxazole 800 mg/160 mg every other day, should be considered for patients at increased risk, e.g. patients with low CD4+ cell counts (< 200 cells/ μ l). For restrictions on use of CYP 3A inhibitors, see Section 4.2.2.1

Cytomegalovirus reactivation during treatment should be treated according to local standards or available guidelines [[R10-4431](#)]. Treatment with BI 836826 must be interrupted until CMV DNA is within limits prior to reactivation.

Infections should be treated according to local guidelines/standard. For restrictions on use of CYP 3A inhibitors, see Section 4.2.2.1.

4.2.1.2.4 Growth factors

The use of growth factors such as granulocyte colony stimulating factor (G-CSF) will be permitted during therapy and should be recorded in the eCRF. However, use of G-CSF is not allowed within 3 days prior to laboratory at screening to reach the inclusion criterion for the neutrophils in patients with pre-existing neutropenia.

4.2.2 Restrictions

4.2.2.1 Restrictions regarding concomitant treatment

Prior antineoplastic therapy for CLL must have been discontinued as specified in inclusion criterion 5, and the patient must have recovered from all clinically relevant reversible toxicities.

No concomitant anti-neoplastic therapy during combination therapy of BI 836826 and ibrutinib is allowed.

Steroids:

Short term glucocorticoid medications may be used as clinically indicated to treat IRRs or autoimmune phenomena, at any dose. Daily oral steroid treatment may be administered at doses equivalent to prednisolone 20 mg per day. All other indications for steroids have to be discussed and agreed upon between investigator and sponsor.

CYP3A Inhibitors:

Due to possible DDIs concomitant use of ibrutinib and CYP3A inhibitors or inducers should be avoided.

Short-term use (i.e. treatment for 7 days or less) of strong CYP3A inhibitors (e.g., antifungals and antibiotics) is permitted while ibrutinib therapy is temporarily discontinued. If use of a strong CYP3A inhibitor is required for an extended period, i.e. more than 7 days, the patient must be discontinued from treatment and trial.

If a moderate CYP3A inhibitor must be used (e.g., fluconazole, darunavir, erythromycin, diltiazem, atazanavir, aprepitant, amprenavir, fosamprevir, crizotinib, imatinib, verapamil, and ciprofloxacin), ibrutinib dose has to be temporarily reduced to 140 mg until the CYP3A inhibitor is no longer needed.

Patients taking concomitant strong or moderate CYP3A inhibitors should be monitored more closely for signs of ibrutinib toxicity.

Anticoagulants and antiplatelet therapy:

Oral anti-coagulants are prohibited throughout the study. If patients require anticoagulation the use of unfractionated heparin or low molecular weight heparin is recommended for the duration of the treatment with ibrutinib. For patients with a platelet count below $50 \times 10^9/L$, decisions on treatment and dosage of anticoagulants and/or antiplatelet therapy should be made on a case by case basis with the utmost caution ([P13-02472](#)). In case the platelet count

declines below $50 \times 10^9/L$, treatment with acetylsalicylic acid should be paused until the platelet count recovers to values $> 50 \times 10^9/L$.

